5.2.2. Analyses of Non-Longitudinal Continuous Data

The non-longitudinal continuous data will be analyzed by Analysis of Covariance (ANCOVA) with treatment as the factor and randomization strata (baseline disease severity and age category) as covariates. When modeling the change from baseline values, the variable for visit will start with the first post-baseline visit, and the actual baseline value will be included as a covariate. At each visit, estimates of least square mean (LSM) values and the LSM differences between the PF-04965842 treated groups and the placebo group will be derived from the model. The corresponding p-values and 95% confidence intervals will also be derived from the model. Estimates of the difference in LSMs along with the two-sided 95% confidence interval will also be provided for the PF-04965842 200 mg QD group versus the PF-04965842 100 mg QD group. No hypotheses will be tested.

5.2.3. Analyses of Longitudinal Continuous Data

Mixed-effect, repeated measures (MMRM) models will be used. The fixed effects of treatment (PF-04965842 200 mg QD and 100 mg QD and the placebo group), visit (Weeks 2, 4, 8 and 12), treatment-by-visit interaction and randomization stratification factors will be included. Visit will be modeled as a categorical covariate. Unstructured covariance matrix will be assumed for the model errors. Compound symmetry covariance matrix will be used if the model with unstructured covariance doesn't converge.

When modeling the change from baseline values, the variable for visit will start with the first post-baseline visit, and the actual baseline value will be included as a covariate. At each visit, estimates of least square mean (LSM) values and the LSM differences between the PF-04965842 treated groups and the placebo group will be derived from the model. The corresponding p-values and 95% confidence intervals will also be derived from the model.

Estimates of the difference in LSMs along with the two-sided 95% confidence interval will also be provided for the PF-04965842 200 mg QD group versus the PF-04965842 100 mg QD dose group. No hypotheses will be tested.

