- q. Pruritus Numerical Rating Scale (NRS) will be assessed using an eDiary, daily during the screening period and from Day 1 to 15. After Day 15, the pruritus NRS will be completed only on study visit days in the eDiary. At the Screening visit, site staff will dispense the ePRO device and review instructions for completion of the subject eDiary for the NRS. At every visit, the study coordinator will review the eDiary for completeness and counsel the subject on how to complete the items in the daily eDiary, if needed.
- r. Pruritus and Symptoms Assessment for Atopic Dermatitis (PSAAD) will be conducted to assess the severity and frequency of pruritus, symptoms and sleep collected daily in a subject e-diary during the screening period and from Day 1 through the End of Study visit in selected countries (See [Section 7.7.7](#)). At the Screening visit, site staff will dispense the ePRO device and review instructions for completion of the subject eDiary for the PSAAD questionnaire. Subjects will be asked to record their assessment in their eDiary once a day before taking the investigational product. At every visit, the study coordinator will review the eDiary for completeness and counsel the subject on how to complete the items in the daily eDiary, if needed.
- s. The contraception check is an opportunity to confirm that contraception, if assigned, is used consistently and correctly. It also facilitates continual reassessment of child-bearing potential in women. This allows for implementing necessary changes to contraception; for example, investigators may need to ensure alternative contraceptive methods if new concomitant disease contraindicates a selected method of contraception, or if a subject is demonstrably no longer of child-bearing status (as per protocol) then they will no longer require contraception. Continual reassessment of contraceptive needs is imperative.
- t. SF-36v2 will be completed by adult subjects only. Adolescents 12-17 years of age will not complete this assessment.
- u. A serum sample will be collected at baseline but analyzed only if the subject has suspected varicella or herpes zoster. In that event, the sample would be analyzed for HSV1, HSV2 and VZV.
- v. Subjects who complete EOT will be assessed for eligibility for participation in long-term extension study B7451015 as noted in [Section 6.2.7](#).
- w. FACIT-F will be completed by adult subjects only. Adolescents 12-17 years of age will complete the Peds-FACIT-F instead.

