1.2.4. Phase 2b in AD (B7451006)

B7451006 was a Phase 2b proof-of-concept trial in adults (ages 18-75) with AD investigating doses of 10, 30, 100, and 200 mg PF-04965842 or placebo taken once daily (QD) for up to 12 weeks. The primary endpoint in this study was the proportion of subjects achieving an IGA score of clear (0), or almost clear (1), and a ≥ 2 -point improvement from baseline at Week 12. The baseline was defined as the IGA score on Day 1 pre-dose.

At Week 12, IGA response rates of PF-04965842 100 mg and 200 mg dose groups were significantly greater than placebo in patients with moderate to severe AD. The IGA response rates of the 200 mg and 100 mg groups were 44.5% and 27.8%, compared to 6.3% in the placebo group, ($P= 0.0032$ and 0.0184 , respectively). The percent change from baseline (% CFB) in EASI scores at Week 12 were significantly higher for both the 200 mg and 100 mg groups compared to placebo ($P<0.0001$ and $P=0.0091$, respectively). PF-04965842 demonstrated a rapid onset of action. In the 200 mg group, IGA and EASI scores improved until week 4 and week 6, respectively, and maintained their effect through 12 weeks of treatment. Response rates at Week 12 for the 10 mg and 30 mg groups were not significantly different from placebo. A key differentiating feature for the JAK1 inhibitor is rapid resolution of itch associated with AD. Significant separation from placebo was achieved for the pruritus NRS score as early as 2 days after initiation of treatment for the 200 mg dose group.

Overall, the results demonstrated dose-dependent increases in responses at Week 12 for key efficacy endpoints (IGA, EASI and pruritus NRS score).

PF-04965842 appeared generally safe and well tolerated in this study. AEs and SAEs were numerically higher in subjects receiving PF-04965842 compared to placebo, but did not appear to increase with dose. The most common AEs were in the infections and infestations, skin and subcutaneous tissue disorders and gastrointestinal disorders system organ class (SOC), and the majority of the AEs were mild. There were 2 cases of herpes zoster, one in the 10 mg group (not treatment related), and one in the 30 mg group (treatment related). There were dose-dependent decreases in platelet counts observed in the study, which plateaued at Week 4, and were not generally clinically relevant. Further details of the clinical Phase 2 development program can be found in the Investigator's Brochure (IB).

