3.2. Key Secondary Endpoints

The key secondary efficacy endpoints are:

- Response based on ≥ 4 points improvement from baseline in the pruritus NRS (NRS4) for severity at Weeks 2, 4 and 12;
- Change from baseline in PSAAD score at Week 12.

Detailed descriptions of how the pruritus NRS and the PSAAD scores are derived are provided in [Appendix 7](#) and [Appendix 8](#) respectively.

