5.1. Hypotheses and Decision Rules

PF-04965842 200 mg QD will be declared superior to placebo if the null hypothesis of no difference between PF-04965842 200 mg QD versus placebo for **both** co-primary endpoints is rejected at the 5% significance level. Similarly, PF-04965842 100 mg QD will be declared superior to placebo if the null hypothesis of no difference between PF-04965842 100 mg QD versus placebo for **both** co-primary endpoints is rejected at the significance level specified below.

[figure not shown]
A sequential Bonferroni-based iterative multiple testing procedure to strongly control the familywise Type 1 error at 5% will be used for testing each of the two PF-04965842 doses (200 mg QD and 100 mg QD) versus placebo on the primary and key secondary endpoints. The procedure belongs to a class of consonant multiple test procedures ([Hommel et al. 2007](#)) which are a subclass of the closed test procedures ([Marcus et al. 1976](#)).

The procedure will first test the Week 12 co-primary endpoints (IGA and EASI-75) for 200 mg QD vs placebo at a 5% significant level. If this hypothesis is not rejected, then no further testing will be conducted. If this hypothesis is rejected, then testing may continue on

two paths depending on the testing for Week 2 NRS4 for severity for 200 mg QD vs placebo at a 2.5% significance level:

- If the hypothesis for the Week 2 NRS4 for severity for 200 mg QD vs placebo is rejected, then the unused alpha level of 2.5% will be passed on to a series of testing in Sequence A (see Figure 2 below) at a 5% significance level. If any hypothesis in this sequence is not rejected, then the procedure stops.
- If the hypothesis for the Week 2 NRS4 for severity for 200 mg QD vs placebo is not rejected, then the series of testing in Sequence A (see Figure 2 below) will be tested at a 2.5% significance level. If any hypothesis in this sequence is not rejected, then the procedure stops. If all hypotheses in this sequence are rejected, then the unused alpha level of 2.5% will be passed on to the testing of hypotheses for Week 2 NRS4 for severity (200 mg QD vs placebo) at a 5% significance level.

Figure 2 Schematic for Multiple Testing Procedure

Hypotheses for all other endpoints not described here are to be tested at the nominal 5% significant level, without making adjustments for multiple comparisons.

090177e1912f28b6\Approved\Approved On: 26-Jun-2019 09:22 (GMT)

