6.3.2. Week 12 Change from Baseline in PSAAD

- Summary: Change from baseline at Week 12;
- Population: FAS, PPAS;
- Statistical Method: MMRM in [Section 5.2.3](#). As PSAAD is collected daily, data will be summarized weekly using a simple average of the values recorded within a week (see [Appendix 8](#)). In the implementation of the MMRM models, data from all weekly visits will be used;
- Missing Data: Observed Data.

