Appendix 8. Pruritus and Symptoms Assessment for Atopic Dermatitis (PSAAD) (e-Diary)

The PSAAD is a daily patient-reported symptom diary. The preliminary version is a 15-item questionnaire that includes 11 items developed to measure symptoms of atopic dermatitis, capturing those identified by patients to be most important, based on a 24-hour recall.

Analysis of the PSAAD will be based solely on these 11 items. CCI

The PSAAD total score will be calculated as the simple arithmetic mean of items 1-11 as listed below. Items 12, 13, 14, and 15 will be only used to further validate PSAAD and they are not the part of the PSAAD scale itself.

For analyses included in this SAP, weekly averages of the PSAAD score will be used. For example, the baseline value is defined as a simple average of all observed values from Day -6 until Day 1, the Week 1 value is defined as a simple average of all observed values from Day 2 until Day 8, the Week 2 value is defined as a simple average of all observed values from Day 9 until Day 15, and so on and so forth up to Week 12.

Pruritus and Symptoms Assessment for Atopic Dermatitis (PSAAD)

Please answer each question by thinking about your skin condition (most often called atopic eczema or atopic dermatitis) over the past 24 hours. This includes today and last night.

For each question, think about all the areas of your body affected by your skin condition and choose the number that best describes your experience.

1) How itchy was your skin over the past 24 hours?

0	1	2	3	4	5	6	7	8	9	10
Not itchy										Extremely itchy

2) How painful was your skin over the past 24 hours?

0	1	2	3	4	5	6	7	8	9	10
Not painful										Extremely painful

3) How dry was your skin over the past 24 hours?

0	1	2	3	4	5	6	7	8	9	10
---	---	---	---	---	---	---	---	---	---	----

Not dry **Extremely dry**

4) How flaky was your skin over the past 24 hours?

0	1	2	3	4	5	6	7	8	9	10
Not flaky										Extremely flaky

5) How cracked was your skin over the past 24 hours?

0	1	2	3	4	5	6	7	8	9	10
Not cracked										Extremely cracked

6) How bumpy was your skin over the past 24 hours?

0	1	2	3	4	5	6	7	8	9	10
Not bumpy										Extremely bumpy

7) How red was your skin over the past 24 hours?

0	1	2	3	4	5	6	7	8	9	10
Not red										Extremely red

8) How discolored (darker or lighter) was your skin over the past 24 hours?

0	1	2	3	4	5	6	7	8	9	10
Not discolored										Extremely discolored

090177e1912f28b6\Approved\Approved On: 26-Jun-2019 09:22 (GMT)

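### If the unstructured MMRM for Week 12 PSAAD fails to converge, the only fallback is compound symmetry, which can misstate the Week 12 standard error in either direction

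*SAP*

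**What the plan says.** SAP 5.2.3 specifies an unstructured covariance for the MMRM. The one alternative is stated as "Compound symmetry covariance matrix will be used if the model with unstructured covariance" does not converge. Inference follows the fitted model: "The corresponding p-values and 95% confidence intervals will also be derived from the model". Neither document names an intermediate structure or a robust variance. Protocol 9.2.4 describes the MMRM without naming a covariance structure.

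SAP 3.2 lists "Change from baseline in PSAAD score at Week 12" as a key secondary endpoint, and SAP 5.1 claims strong familywise control at 5% over the primary and key secondary endpoints. The co-primary endpoints and the other key secondary endpoint (NRS4) are tested by CMH, so PSAAD is the only endpoint in that family that depends on the MMRM.

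SAP 5.2.3 lists four visits (Weeks 2, 4, 8 and 12), but SAP 6.3.2 overrides this for PSAAD: "In the implementation of the MMRM models, data from all weekly visits will be used". Appendix 8 builds the weekly series, in which "the Week 1 value is defined as a simple average of all observed values from Day 2 until Day 8", and carries it to Week 12. The Protocol Schedule of Activities (footnote r) has PSAAD collected "from Day 1 through the End of Study visit in selected countries", so the PSAAD sample may be smaller than the planned 375.

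**The concern.** Compound symmetry imposes one variance on all weeks and one correlation on all pairs of weeks. The Week 12 contrast then takes its standard error from the average week. Residual variance need not be constant here: the model adjusts for baseline, and if a subject's correlation with baseline weakens over time, the unexplained variance grows. It could also shrink, for example if scores bunch near zero under treatment.

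PSAAD is where the fallback matters most. It has 78 covariance parameters, against 4 × 5 / 2 = 10 for a four-visit endpoint and 2 under compound symmetry. On the fallback branch, a rising variance would leave the claimed Type I error control unassured, and a falling variance would cost power. Replacing the structure after seeing the data would be a data-driven choice in a controlled test.

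**Working it through.** **What the plan gives.** There is no SD, standard error or power for PSAAD to reproduce. The stated powers concern the co-primary endpoints. They reproduce (150 vs 75, two-sided 5%, pooled: 97.8% for IGA, 99.8% for EASI-75) and do not bear on this point. All variance, correlation and dropout inputs below are assumptions.

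**Complete data.** With a separate mean for each arm and week, the compound-symmetry variance of the Week 12 contrast uses the mean of the 12 weekly variances. The true variance uses Week 12's own. Define

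R = Week 12 residual variance / mean weekly residual variance,

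true error = 2 × (1 − Φ(z / √R)), with z = 1.960 at 5% and 2.241 at 2.5%.

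The 2.5% level applies to Sequence A if Week 2 NRS4 for 200 mg is not rejected. With unit total variance and correlation ρ with baseline, weekly residual variance is 1 − ρ².

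Worked case, ρ falling linearly from 0.8 at Week 1 to 0.4 at Week 12: Week 12 variance = 1 − 0.16 = 0.840; mean of 1 − ρ² over 12 weeks = 0.624; R = 0.840 / 0.624 = 1.346; √R = 1.160; 1.960 / 1.160 = 1.690; true error 9.1%.

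| Assumed profile | Week 12 variance | Mean variance | R | True error at 5% | At 2.5% |
|---|---|---|---|---|---|
| ρ 0.7 to 0.6, linear | 0.640 | 0.577 | 1.110 | 6.3% | 3.3% |
| ρ 0.8 to 0.4, linear | 0.840 | 0.624 | 1.346 | 9.1% | 5.3% |
| ρ 0.9 to 0.4, linear | 0.840 | 0.553 | 1.519 | 11.2% | 6.9% |
| ρ 0.8 to 0.4, plateau from Week 4 | 0.840 | 0.766 | 1.097 | 6.1% | 3.2% |
| ρ 0.8 to 0.4, plateau from Week 6 | 0.840 | 0.731 | 1.150 | 6.8% | 3.7% |
| SD 2.2 to 1.6, linear | 2.560 | 3.645 | 0.702 | 1.9% | 0.8% |
| Constant variance | – | – | 1.000 | 5.0% | 2.5% |

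The plateau rows are motivated by the Phase 2b course in Protocol 1.2.4 for the 200 mg group, where "IGA and EASI scores improved until week 4 and week 6, respectively, and maintained their effect through 12 weeks of treatment". Those are other endpoints, so this is suggestive only. Starting the 0.8-to-0.4 decline at Week 0 instead of Week 1 gives 8.6% rather than 9.1%.

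**Constant variance with dropout.** If correlation decays with lag, compound symmetry overstates what earlier weeks say about a missing Week 12. With AR(1) correlation 0.93 and 10%, 15% and 20% dropout, R = 1.040, 1.063 and 1.087, giving 5.5%, 5.7% and 6.0%. With AR(1) 0.85 and 20% dropout, R = 1.102, giving 6.2%. At nominal 2.5% the range is 2.8% to 3.3%.

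**Simulation.** Compound symmetry fitted by REML, 12 weeks, 150 vs 75, AR(1) 0.93, 15% dropout, 4,000 null runs per setting (Monte Carlo SE about 0.35 points near 5% and 0.5 near 10%):

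| Variance profile | Model-based SE, 5% (2.5%) | Sandwich SE, 5% |
|---|---|---|
| Linear rise | 10.8% (6.6%) | 5.5% |
| Plateau at Week 6 | 7.1% (4.1%) | 4.7% |
| Constant | 5.8% (2.9%) | 5.2% |
| Falling | 2.3% (1.1%) | 5.1% |

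At nominal 2.5% the sandwich errors run from 2.4% to 2.7%.

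**Independent check.** Separate code used three arms (75/150/150), baseline and two strata as covariates, AR(1) 0.9, 20% random dropout, and 1,000 trials with two contrasts each. Error at nominal 5% was 8.5% for SD rising 1.7 to 2.1, 6.8% for constant SD, 3.0% for SD falling 2.1 to 1.7, and 4.7% when the true covariance was compound symmetric. Steeper assumed profiles gave 16.3% (SD 1.2 to 2.4) and 1.3% (2.4 to 1.2).

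**The case against.** The strongest reply is that the branch may never be used. An unstructured 12-visit REML fit was simulated in the linear-rise scenario with AR(1) 0.93 and 15% dropout, at 150/150/75, 75/75/38 and 40/40/20 subjects, with 0% and 5% extra intermittent missingness. It converged in 600 of 600 fits (100 per setting). A weekly average is also missing only when no day of that week is recorded. The unconditional excess is the probability of non-convergence times the conditional excess. If non-convergence were 1% to 2% (assumed), the 9.1% and 11.2% cases would add about 0.01 × 4.1 = 0.04 to 0.02 × 6.2 = 0.12 percentage points to a 5% test.

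The largest figures also need a baseline correlation still falling at Week 12; the plateau cases are milder and the direction is unknown. PSAAD is reached only after the 200 mg co-primaries are rejected, so a false rejection needs a drug that works on IGA and EASI-75 but not on PSAAD. Finally, sandwich errors do not remove bias from a wrong covariance when dropout depends on outcome.

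Most of this stands as a limit on likelihood and severity. The convergence runs used simulated normal data without strata or baseline covariates, so they do not show that the fallback is unreachable, and the SAP itself provides for it. On outcome-dependent dropout, one check of compound symmetry with sandwich errors gave 5.9% (5.0% under random dropout). Another, with rising variance, gave 5.0%, against 11.0% for the model-based error. The caveat is real but small in these checks.

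**Conclusion.** The concern holds as a conditional point. If the unstructured model converges, nothing changes. If it does not, the planned fallback gives a valid Week 12 standard error when variance is constant and data are complete, or when the covariance really is compound symmetric, but not in general. Under the main assumed profiles, true error at nominal 5% ranges from about 2% (falling variance) to about 11% (steep linear rise), with 6% to 7% in the plateau cases. Which applies cannot be told from the documents, which give no PSAAD variances, correlations or dropout. The chance of non-convergence cannot be derived from them either. PSAAD's place in Sequence A could not be checked because Figure 2 is not reproduced in the text available; its membership of the controlled family is clear from SAP 5.1 and Protocol 9.2.2. The change is worth making because it is cheap, not because failure is expected. Confidence is medium.

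**What to change.** In SAP 5.2.3, replace the single fallback with a fixed order: unstructured, then heterogeneous Toeplitz, then heterogeneous AR(1), with compound symmetry last. State that empirical (sandwich) standard errors apply whenever a structured covariance is used. Keep all weekly PSAAD data as 6.3.2 specifies, and note in 5.2.3 that its four-visit list does not apply to PSAAD. Make the change before unblinding.

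The cost is SAP wording and standard software options. There is no effect if the unstructured model converges. On a fallback, the standard error may be larger than under model-based compound symmetry. Sandwich errors can be slightly liberal in small samples: in the linear-rise scenario, simulated error was 5.0% at 75 vs 38 and 5.7% at 40 vs 20, against 10.6% and 9.7% for model-based compound symmetry.

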9.2.4. Analysis of Secondary Endpoints

The key secondary endpoints which are expressed as proportions such as the proportion of subjects achieving a 4-point improvement from baseline in the pruritus NRS measure will be analyzed using the same method as the for co-primary endpoints in [Section 9.2.3](#). This would also apply to any other binary endpoint in the study, such as EASI50, EASI90, SCORAD50, SCORAD75 or the proportion of subjects with PtGA of AD of clear (0) or almost clear (1) and ≥ 2 point improvement from baseline over 12 weeks.

For continuous endpoints, such as percent change from baseline in the EASI total score or change from baseline in PSAAD, DLQI/CDLQI, POEM, HADS, SF-36v2, FACIT-F/Peds-FACIT, EQ-5D-5L/EQ-5D-Y and SCORAD and change from baseline in the pruritus severity and frequency using the NRS measure at all scheduled time points, a mixed-effect model with repeated measures (MMRM) will be used. This model will include the factors (fixed effects) for treatment group, randomization strata (age group, disease severity), visit, treatment-by-visit interaction, and relevant baseline value. Within the framework of MMRM, the treatment difference will be tested at the pre-specified primary time point, Week 12, as well as at the other time points by time point-specific contrasts from the MMRM model.

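### The MMRM fits one baseline slope for all visits; if that slope changes by Week 12, the continuous Week 12 contrasts, including PSAAD, lose some precision that a baseline-by-visit term would recover at almost no cost

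*SAP*

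**What the plan says.** SAP 5.2.3 names the fixed effects of the MMRM as treatment, visit and two further items: "treatment-by-visit interaction and randomization stratification factors will be included". For change from baseline it adds that "the actual baseline value will be included as a covariate". Protocol 9.2.4 gives the same list, ending with "visit, treatment-by-visit interaction, and relevant baseline value". The Statistical Methods part of the protocol summary agrees. None of these places mentions a baseline-by-visit term, so as written the model has a single baseline coefficient.

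On covariance, SAP 5.2.3 says "Unstructured covariance matrix will be assumed for the model errors". The fallback is: "Compound symmetry covariance matrix will be used if the model with unstructured covariance" fails to converge.

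SAP 3.2 lists "Change from baseline in PSAAD score at Week 12" as a key secondary endpoint. SAP 6.3.2 analyses it with this MMRM on weekly averages: "In the implementation of the MMRM models, data from all weekly visits will be used". SAP 5.1 puts the primary and key secondary endpoints under 5% familywise control. The sequence figure is not available, but Protocol 9.2.2 counts five key hypotheses per dose. That fits the co-primary pair, pruritus response at Weeks 2, 4 and 12, and PSAAD (1 + 3 + 1 = 5).

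**The concern.** A single coefficient assumes that a one-point difference at baseline predicts the same difference in change at the first post-baseline visit as at Week 12. If the link with baseline weakens over time, the correct coefficient for change becomes more negative by Week 12. Under an unstructured covariance the fitted common slope is pulled towards early visits, where baseline explains most and the residual variance is smallest. The unexplained part stays in the Week 12 residual.

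The stake is precision at the time point that Protocol 9.2.4 designates as primary for continuous endpoints. Only PSAAD carries controlled alpha; the other MMRM endpoints are tested at a nominal 5%. PSAAD is collected only in selected countries, so its sample may be below 150/150/75. Neither document states a power for it. In the fixed sequence, a PSAAD test that fails also stops whatever follows it.

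**Working it through.** **The plan's own figures.** These are for the binary co-primaries with 75 placebo and 150 active subjects at two-sided 5%. For IGA, 6% vs 26%, the pooled rate is (4.5 + 39)/225 = 0.193. The null SE is √(0.193 × 0.807 × (1/75 + 1/150)) = 0.0559 and the alternative SE is √(0.06 × 0.94/75 + 0.26 × 0.74/150) = 0.0451. Power = Φ((0.20 − 1.96 × 0.0559)/0.0451) = 97.8%, consistent with the stated 95% or more. EASI-75 (15% vs 45%) gives 99.8%, consistent with 99% or more. The joint bound 0.95 + 0.99 − 1 = 94% also matches. None of these depends on the MMRM. No SD, correlation, effect size or power is given for PSAAD or any other MMRM endpoint, so everything below rests on assumptions.

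**Formula.** Take the baseline variance as 1. Let β_t be the slope of the visit-t score on baseline; the slope for change is β_t − 1, so differences between visits are the same. Let C be the residual covariance given baseline. The common slope under unstructured covariance is b = 1′C⁻¹β / 1′C⁻¹1. Relative to a model with visit-specific slopes, the Week 12 variance ratio is 1 + (β₁₂ − b)²/C₁₂,₁₂.

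**Worked case.** Assumptions: visits at Weeks 2, 4, 8 and 12; equal SDs; baseline correlation falling linearly from 0.8 to 0.4; post-baseline correlation 0.90 per week apart; complete data.
- Slopes: 0.80, 0.72, 0.56, 0.40.
- Residual variance: 1 − 0.64 = 0.36 at Week 2 and 1 − 0.16 = 0.84 at Week 12.
- Weights from C⁻¹: 0.57, 0.11, 0.13, 0.19, so b = 0.456 + 0.079 + 0.073 + 0.076 = 0.684.
- Variance ratio: 1 + (0.40 − 0.684)²/0.84 = 1.096, so the SE is 4.7% larger.

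**Range.** The table gives the increase in Week 12 SE with four visits. Where two values are shown, the post-baseline correlation is 0.90 and 0.95 per week.

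| Baseline correlation, first visit to Week 12 | Unstructured, equal SDs | Unstructured, SD grows 30% by Week 12 | Compound-symmetry slope (plain average), equal SDs |
|---|---|---|---|
| 0.6 to 0.4 | 0.8%, 0.9% | 0.1%, 0.2% | 0.7% |
| 0.7 to 0.4 | 2.1%, 2.8% | 0.7%, 1.0% | 1.6% |
| 0.8 to 0.4 | 4.7%, 7.0% | 1.8%, 2.8% | 2.8% |
| 0.9 to 0.4 | 9.3%, 16.3% | 3.9%, 6.2% | 4.4% |

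Twelve weekly visits, the PSAAD layout, give nearly the same values (0.8 to 0.4, equal SDs: 4.5% and 6.5%). These are not upper bounds. At 0.97 per week the loss is larger: a fall from 0.7 to 0.3 gives a variance ratio of 1.17 to 1.19.

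**Validity.** Simulation used 3,000 trials per case, 150 vs 75, four visits, unstructured covariance and complete data. The common-slope estimates averaged 0.397 to 0.403 SD against a true 0.400. Rejection under the null was 3.7% to 5.2%.

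**Chance imbalance.** With 150 vs 75, the SD of the baseline difference is √(1/150 + 1/75) = 0.141 baseline SD. In the worked case the typical shift is 0.284 × 0.141 = 0.040. Its square, 0.0016, divided by the fully adjusted variance 0.84 × 0.02 = 0.0168, is 0.096. That is exactly the inflation already found.

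**The case against.** The best reply is that nothing here is an error. The model is pre-specified and agrees between protocol and SAP, and its inference is valid under randomization with complete data. That the baseline correlation fades is an assumption; neither document reports it. What matters is the slope, and entry thresholds on severity can narrow the baseline spread, making a larger SD at Week 12 plausible. The table shows how far that shrinks the loss. A twelve-visit unstructured matrix has 12 × 13/2 = 78 parameters. If it does not converge, the fallback applies and the loss is smaller again. Stratification by baseline severity also balances part of the baseline variation. All of this stands and limits the size of the point. It does not set the size to zero, and it gives no reason to prefer the common slope.

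A reader might infer stronger claims that the documents do not support:
- **Bias or inflated type I error.** With complete data there is neither.
- **Chance baseline imbalance as a second harm**, given 75 placebo subjects. It is the same loss, as shown above.
- **A stated drop in PSAAD power.** Any such figure must start from a power that the plan never gives.
- **Failure of the missing-at-random argument in SAP 5.3.2.** One assumed dropout pattern (11% at random on active, 21% score-driven on placebo) moved the estimate by −0.048 SD in the drug's favour when there was no effect. With score-driven dropout in both arms, the estimate was −0.413 against a true −0.400. The documents give no dropout rates or pattern, so this shows a possibility and is not a finding about this trial.

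**Conclusion.** The point holds as a precision refinement of undetermined size. As written, the MMRM has one baseline slope. If the slope at Week 12 differs from the earlier ones, the Week 12 contrasts are under-adjusted. On the assumptions tabulated, the cost ranges from under 1% of the SE to about 16%. For a fall from 0.8 to 0.4 it is about 2-7%, equivalent to losing 1 − 1/1.018² = 3.5% to 1 − 1/1.070² = 12.7% of the subjects. If the slope is constant there is nothing to gain and essentially nothing to lose.

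The co-primary CMH tests, the sample size and the stated power are untouched. So are the Week 12 FACIT-F and SF-36v2 analyses, which use a single-visit ANCOVA under SAP 5.2.2 and therefore already have their own Week 12 slope.

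**What to change.** Before unblinding, add a baseline-by-visit interaction to the fixed effects in SAP 5.2.3 for every change-from-baseline MMRM endpoint (SAP 6.3.2, 6.4.6 and 6.5.1). Name PSAAD explicitly in 6.3.2. Fix the term in advance; do not make it depend on observed correlations. The cost is 4 − 1 = 3 degrees of freedom with four visits, or 12 − 1 = 11 with twelve weekly averages. A SAP amendment is enough, because Protocol section 9 requires a protocol amendment only for major changes to the co-primary endpoint definitions or their analyses.
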